14. DEFINITIONS, RECORDING, AND REPORTING OF ADVERSE EVENTS

14.1. Definition of Adverse Events

According to International Council for Harmonisation (ICH) guidance E2A, Clinical Safety Data Management: Definitions and Standards for Expedited Reporting, an AE is any untoward medical occurrence in a patient or clinical investigation patient administered a pharmaceutical product and which is not necessarily required to have a causal relationship with this treatment. An AE can therefore be any unfavorable and unintended sign (including an abnormal laboratory finding, for example), symptom, or disease temporally associated with the use of a medicinal product, whether or not considered related to the medicinal product.

A TEAE is an AE that either commenced following initiation of study treatment or was present prior to study treatment but increased in frequency or severity following initiation of study treatment.

14.2. Adverse Event Recording

14.2.1. Coding the Adverse Event

Standard medical terminology should be used in describing AEs. MedDRA v24.1 and WHODRUG Global (B3 format) will be used as the standard coding dictionary for AEs and in describing the patient's medical history, and the WHO Drug Dictionary will be used to code concomitant medications. Informal descriptions should be avoided.

14.2.2. Severity of Adverse Event

AEs should be graded as mild, moderate, or severe using the following definitions.

- ***Mild:*** Awareness of signs or symptoms, but easily tolerated and of minor irritant type causing no loss of time from normal activities. Symptoms do not require therapy or a medical evaluation; signs and symptoms are transient.
- ***Moderate:*** Events introduce a low level of inconvenience or concern to the participant and may interfere with daily activities, but are usually improved by simple therapeutic measures; moderate experiences may cause some interference with functioning.
- ***Severe:*** Events interrupt the participant's normal daily activities and generally require systemic drug therapy or other treatment; they are usually incapacitating.

To make sure there is no confusion or misunderstanding of the difference between the terms "serious" and "severe," which are not synonymous, the following note of clarification is provided. The term "severe" is often used to describe the intensity (severity) of a specific event (as in mild, moderate, or severe myocardial infarction); the event itself, however, maybe of relatively minor medical significance (such as severe headache). This is not the same as "serious," which is based on patient/event outcome or action criteria usually associated with events that pose a threat to a patient's life or functioning. Seriousness (not severity) serves as a guide for defining regulatory reporting obligations.

14.2.3. Relationship of Adverse Events to Study Drug

The Investigator will assess the potential relationship of the AE to study drug using the following descriptions.

- ***Not Related:*** This category applies to an AE that is clearly not related to the study drug beyond a reasonable doubt. That is, another cause of the event is most plausible; and/or a clinically plausible temporal sequence is inconsistent with the onset of the event and the administration of study drug and/or a causal relationship is considered biologically implausible.
- ***Unlikely Related:*** This category applies to an AE that could reasonably be considered caused by something else, and where there is no known or expected response pattern to the suspected study drug.
- ***Possibly Related:*** This category applies to an AE that follows a reasonable temporal sequence from administration of the study drug and that follows a known or expected response pattern to the suspected study drug, but that could readily have been produced by a number of other factors.

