5.2. Background of TNX-102 SL

TNX-102 SL (cyclobenzaprine HCl sublingual tablets) is being developed through 505(b)(2) New Drug Applications (NDAs) for FM, post-traumatic stress disorder (PTSD), Agitation in Alzheimer's Disease, and Alcohol Use Disorder using AMRIX (extended release [ER] capsule, 30 mg; [AMRIX® Prescribing Information, 2019](#)) as the reference listed drug. We are currently also developing TNX-102 SL for the treatment of multi-site pain in PASC.

The TNX-102 SL is a formulation containing 2.8 mg cyclobenzaprine HCl [3-(5H-dibenzo[a,d]cycloheptene-5-ylidene)-N,N-dimethyl-1-propanamine hydrochloride] for sublingual (SL) administration. The active ingredient in TNX-102 SL, cyclobenzaprine HCl (CBP), has been approved for use in the US since 1977, originally as FLEXERIL® 10-mg oral tablets indicated as an adjunct to rest and physical therapy for the relief of muscle spasm associated with acute, painful musculoskeletal conditions. The usual dose for this indication is 30 mg or 15 mg per day taken as 10 mg three times daily (TID) or 5 mg TID, respectively ([FLEXERIL® Prescribing Information, 2013](#)). The FLEXERIL® brand of immediate-release (IR) CBP tablets was discontinued in May 2013. Generic CBP is available and marketed in a variety of strengths, including 5-, 7.5- and 10-mg IR tablets. AMRIX® ([AMRIX® Prescribing Information, 2019](#)), an ER capsule of CBP, was approved in 2007 in the US through an NDA and is currently available in 15 and 30 mg, taken once a day for the same indication as FLEXERIL® in the US. Both FLEXERIL® and AMRIX® are indicated for 2–3 weeks use only. No CBP product has been approved for use in PASC by the Food and Drug Administration (FDA), Health Canada, or in any other country.

In addition to its therapeutic effects on muscle spasm, CBP also exhibits functional antagonism of 5 HT2A, α 1-adrenergic, H1-histaminergic, and M1-muscarinic acetylcholine receptors, and these actions may underlie its putative ability to improve sleep quality. TNX-102 SL is a low-dose sublingual formulation of CBP being developed to provide greater diurnal variation in peak-to-trough drug levels to enhance nocturnal treatment effects while minimizing daytime side effects.

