13.7. Safety Analyses

Safety analyses will be performed using the Safety Population. The analysis of safety assessments in this study will include summaries of the following safety and tolerability data collected for each patient:

- Incidence of AEs
- Changes from Baseline in clinical laboratory tests
- Changes from Baseline in vital signs
- Changes from Baseline in physical examination findings including examination of the oral cavity
- Monitoring suicidality using the C-SSRS

All AEs, treatment-emergent adverse events (TEAEs), and SAEs will be coded using the MedDRA.

An AE summary table will be presented for the following:

- All TEAEs
- TEAEs by severity
- TEAEs leading to study drug discontinuation
- TEAEs by relationship
- SAEs
- Oral cavity TEAEs
- Oral cavity TEAEs by severity

Summaries of incidence rates (frequencies and percentages), of individual AEs by MedDRA SOC and preferred term will be prepared. Such summaries will be displayed for all TEAEs, oral cavity TEAEs, TEAEs by maximum severity, and TEAEs by strongest relationship to study drug.

Each patient will be counted only once within each summation level (SOC; preferred term). If a patient experiences more than one TEAE within each summation level, the TEAE with the strongest relationship or the maximum severity, as appropriate, will be included in the summaries of relationship and severity.

In the AE data listings, all AEs will be displayed.

Laboratory data include analytes for chemistry and hematology, and these will be summarized by treatment and visit for the Safety Population. Descriptive summaries of actual values and changes from Baseline will be presented by study visit and last available assessment for each clinical laboratory analyte and each treatment group. 95% confidence intervals will be presented for change from Baseline.

Laboratory values will be displayed in the data listings with their corresponding normal ranges, and those values that are outside the normal range will be flagged. For each laboratory analyte, shifts in assessments of abnormality from Baseline to each scheduled time point will be presented in shift tables.

A by-patient listing of all clinical laboratory data will also be provided.

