8.3 Safety Endpoints

To handle missing or partial AE and concomitant medication dates, the following rules will be applied.

For partial start dates:

1. If the year is unknown, then do not impute the date but assign a missing value.
2. If the month is unknown, then:
 - a. If the year matches the year of the first dose date, then impute the month and day of the first dose date.
 - b. Otherwise, assign “January.”
3. If the day is unknown, then:
 - a. If the month and year match the month and year of the first dose date, then impute the day of the first dose date.
 - b. Otherwise, assign “01.”

For partial end dates:

1. If the year is unknown, then do not impute the date but assign a missing value.
2. If the month is unknown, then assign “December.”
3. If the day is unknown, then assign the last day of the month.

Adverse events are categorized as pre-treatment adverse events or treatment-emergent adverse events based on the response to the CRF question “Did the AE start prior to the first dose?”

The missing severity of an AE will be imputed to “severe”; the missing relationship to study drug of an AE will be imputed to “possibly related”.

After implementing the rules above, the following strategy will be used to determine whether medications with missing start or stop dates are prior or concomitant medications:

1. If the start date and stop date are both missing, then the most conservative approach is taken and the medication is considered to be a concomitant treatment.
2. If the start date is missing but the stop date is not missing and is after the day of first study dose administration, then the most conservative approach is taken and the medication is considered to be concomitant.
3. If the start date is missing but the stop date is not missing and is on or before the day of first study dose and after the date of signed informed consent, then the medication is considered to be a prior treatment.
4. If the start date is not missing but the stop date is missing, then the most conservative approach is taken and the medication is considered to be concomitant.

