11.1.3 Oral TEAEs

In light of the study drug's sublingual route of delivery, patients will undergo a detailed examination of the oral cavity at screening and brief examinations at all other visits.

AEs involving the oral cavity may be spontaneously reported by the patient, observed during an oral cavity examination, or both. Oral cavity AEs will be identified by a "yes" response to the CRF question, "Is the AE in the oral cavity?" Additional information will be collected on oral cavity AEs (based on a "yes" response to the above question), including whether the AE occurs immediately or very soon after dosing, an approximation of the duration of the AE (less than or greater than 60 minutes), and whether the AE is still present the next morning upon awakening.

A separate by-patient listing of oral cavity AEs (including pre-treatment oral cavity AEs) will be provided.

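### The causality scale has no level for an adverse event with no alternative cause, and it keeps a reaction that is neither known nor expected out of 'Possibly Related'

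*Protocol*

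**What the plan says.** Protocol 14.2.3 directs that "The Investigator will assess the potential relationship of the AE to study drug using the following descriptions", and then prints three levels.

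- **Not Related.** The lead sentence is strict: "This category applies to an AE that is clearly not related to the study drug beyond a reasonable doubt". The explanation that follows is looser. It accepts that another cause is the most plausible one, and/or that the timing does not fit, and/or that a causal link is biologically implausible.
- **Unlikely Related.** Something else could reasonably be the cause, "where there is no known or expected response pattern to the suspected study drug".
- **Possibly Related.** The timing is reasonable and the event is one "that follows a known or expected response pattern to the suspected study drug, but that could readily have been produced by" several other factors.

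No level above 'Possibly Related' is printed.

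The rating feeds planned outputs. Protocol 13.7 and SAP 11.1 both call for "TEAEs by strongest relationship to study drug", and each patient counts once per system organ class or preferred term, at the strongest rating. SAP 8.3 adds that "the missing relationship to study drug of an AE will be imputed to" 'possibly related'. The same sentence sends a missing severity to 'severe', the top severity grade in Protocol 14.2.2. The SAP thus treats 'possibly related' as the worst case, which agrees with a three-level scale.

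**The concern.** A causality scale should give every event exactly one level, and the level should rise as the case against the drug gets stronger. The printed definitions do neither. The top level requires a competing explanation, so the events most clearly attributable to the drug, those with no competing explanation, have nowhere to go. The top level also requires a known or expected pattern. That makes expectedness a condition of causality, when the two are separate questions.

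Both situations can arise here. The protocol foresees tingling, numbness and odd taste following a sublingual dose (11.2.4, 11.9, 12.2.2), and the SAP records "whether the AE occurs immediately or very soon after dosing" for oral events. Such an event can have a familiar pattern, close timing and no other explanation. As for new reactions, the trial gives 14 weeks of sublingual dosing in a new indication, whereas Protocol 5.2 notes that the two branded oral products "are indicated for 2–3 weeks use only".

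At stake is whether the by-relationship tables mean the same thing from site to site, and whether they give a fair picture of reactions not yet described.

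**Working it through.** The protocol states no figure to reproduce. The check sets the definitions side by side and tests whether they cover every event.

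**Step 1. Conditions for each level (Protocol 14.2.3).**

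| Level | Timing | Response pattern | Other cause |
|---|---|---|---|
| Possibly Related | Reasonable | Known or expected | Required |
| Unlikely Related | Not stated | Neither known nor expected | Required |
| Not Related | Poor fit is one ground | Not stated | Being most plausible is one ground |

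Biological implausibility is a further ground for 'Not Related'.

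**Step 2. Take an AE with reasonable timing and a biologically plausible link, and cross the two remaining features.**

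| Pattern | Another reasonable cause? | Level that fits |
|---|---|---|
| Known or expected | Yes | Possibly Related |
| Neither | Yes | Unlikely Related (Not Related if that cause is most plausible) |
| Known or expected | No | None |
| Neither | No | None |

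Both empty rows are those with no alternative cause. Only the first row reaches 'Possibly Related'. The second row differs from the first only in whether the reaction is already known or expected, so novelty alone lowers the rating.

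**Step 3. Overlap.** In the first row, if the other cause is also the most plausible one, the explanation under 'Not Related' is met as well, although its lead sentence sets a stricter test. One event can then satisfy the highest and the lowest level.

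**Step 4. What happens to an event in an empty row.** The investigator may

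- leave the rating blank, in which case SAP 8.3 makes it 'possibly related';
- choose 'Possibly Related' as the nearest fit; or
- choose 'Unlikely Related' as the nearest fit.

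The first two routes put the event at the top of the scale and the third does not. The same event can therefore land in different columns of the table according to local habit.

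**Step 5. What does not use the rating.** The summaries of all TEAEs, TEAEs by severity, TEAEs leading to discontinuation, SAEs and oral-cavity TEAEs (Protocol 13.7, SAP 11.1) are not split by relationship. Protocol 14.3 requires sites to report every SAE, and every death whether or not it is attributed to treatment. There is one narrow exception: SAP 11.1 lets a recurrent pre-treatment event become treatment-emergent if its relationship rating rises. Protocol 14.1 has no such clause.

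**The case against.** The strongest case against acting is that little depends on the rating. In a randomised, placebo-controlled trial a new reaction would be looked for as an imbalance between arms in the overall TEAE tables, and those do not depend on the causality label. Oral events have their own case report form (CRF) flag, follow-up questions, tables and listing (SAP 11.1.3). This stands, and it confines the harm to individual ratings and the by-relationship tables.

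Several stronger readings are tempting, and the documents do not support them.

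- *Any new reaction lacks a category.* This is so only when there is also no other cause. With another reasonable cause it has a level, 'Unlikely Related'.
- *Every undescribed reaction is barred from 'Possibly Related'.* The text says known **or expected**. A reaction not yet described, but foreseeable from the receptor actions listed in Protocol 5.2, could qualify.
- *Such an event cannot be counted as drug-related.* A blank rating is imputed to the top level, and an investigator may choose that level as the nearest fit.
- *Serious new reactions would go unreported.* Site reporting in Protocol 14.3 has no relationship condition. The criteria for expedited reporting are not spelled out there, so no effect of an 'Unlikely' rating on that step can be shown.
- *Half of all events have no level.* The four rows are logical cases, not equally frequent ones. Protocol 12.2.1 notes that Long COVID symptoms are many and fluctuate, so events with no other plausible cause may be uncommon.

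**Conclusion.** The point holds in limited form. As printed, the scale has no level for an AE with reasonable timing and no alternative cause. It also keeps a reaction that is neither known nor expected out of 'Possibly Related', sending it to 'Unlikely Related' when another reasonable cause exists. The consequence is inconsistent causality ratings and by-relationship tables that may understate new reactions. The size cannot be estimated, because the documents give no frequency of AEs by pattern or by alternative cause.

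The conclusion assumes that investigators apply the definitions as written and that the three printed levels are the whole scale, as the SAP 8.3 imputation suggests. If a higher level existed, it might cover events with no alternative cause. A reaction neither known nor expected that has another possible cause would still be excluded from 'Possibly Related'.

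**What to change.** Keep three levels in Protocol 14.2.3 and reword them:

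- **Not Related:** timing is incompatible, the relationship is biologically implausible, or another cause is established.
- **Unlikely Related:** another cause is clearly more likely. Drop the condition about the response pattern.
- **Possibly Related:** timing is reasonable and a causal role of study drug is a reasonable possibility, whether or not the reaction is already known or expected, and whether or not other factors could also explain it.

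To prevent gaps and overlap, tell sites to test the levels in that order and to rate whatever remains as 'Possibly Related'. Both empty rows of the table above then become 'Possibly Related', and the other two rows are decided by the strength of the competing cause and not by novelty.

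No CRF level is added. The SAP 8.3 imputation needs no edit and remains the worst case. The SAP 11.1 tables keep their layout.

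The costs are a wording amendment, site retraining and slightly more events rated related in both arms. Timing also matters: SAP version 1.1 is dated 20 June 2023, and the Protocol synopsis estimated first enrolment in August 2022, so some AEs may already carry ratings under the printed wording. Those should be re-rated, or identified so that the by-relationship tables can separate them.

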14.3. Serious Adverse Events (SAEs) and Serious Adverse Drug Reactions

Any SAE that occurs at any time during the study, including a clinically significantly abnormal laboratory test result that is considered serious, must be reported to Tonix or its designee(s) so that Tonix may comply with regulatory obligations. If the SAE is life-threatening or fatal, it must be reported to Tonix or its designee(s) immediately, by facsimile and telephone. For these and all other SAEs, an SAE report form must be completed and sent by facsimile or email to Tonix or its designee(s) within 1 working day of the site's initial awareness of the event. These requirements apply equally to all patients, regardless of the study phase or the at-risk patient's treatment assignment or dosage.

An SAE (experience) or reaction is any untoward medical occurrence that, at any dose:

[figure not shown]
- Results in death,
- Is life-threatening,
- Requires in-patient hospitalization or prolongation of existing hospitalization,
- Results in persistent or significant disability/incapacity,
- Is a congenital anomaly/birth defect, or
- Is an important medical event.

NOTE: The term “life-threatening” in the definition of “serious” refers to an event in which the patient was at risk of death at the time of the event. It does not refer to an event that hypothetically might have caused death if it were more severe.

Medical and scientific judgment should be exercised in deciding whether expedited reporting is appropriate in other situations, such as important medical events that may not be immediately

life-threatening or result in death or hospitalization but may jeopardize the patient or may require intervention to prevent one of the other outcomes listed in the definition above. *These should also usually be considered serious.* Examples of such events are intensive treatment in an emergency room or at home for allergic bronchospasm, blood dyscrasias or convulsions that do not result in hospitalization, or development of drug dependency or drug abuse. The development of C-SSRS suicidal ideation type 4 (intent) or type 5 (specific plan and intent) any time after consenting to the study should always be reported as an SAE. Additionally, since only Types 1 and 2 are allowed at Screening or Baseline, the development of C-SSRS Type 3 (method but no plan or intent) after consenting should always be reported as an AE.

Any death occurring during the study, during the per-protocol follow-up period, or reported to the Investigator after study participation (no required post-study time limit) must be reported to Tonix or its designee(s) immediately, whether or not it is considered treatment-related. Initial SAE reports must be followed by detailed descriptions. These should include copies of hospital case records and other documents when requested. Telephone reports must be confirmed promptly either by facsimile or by e-mail. For reporting SAEs, Tonix's designated Medical Monitor should be called, and the relevant forms submitted to Premier pharmacovigilance within 24 hours of the site's awareness of the SAE. The contact information for the Medical Monitors is as follows:

The Investigator, or the Sponsor or designee in the case of a central institutional review board (IRB), also must notify the ethics committee (EC)/IRB of the occurrence of the SAE, in writing, as soon as is practicable and in accordance with local law. A copy of this notification must be provided to Tonix or its designee.

In the event of an SAE that meets the criteria for expedited reporting, an investigational new drug (IND) Safety Report will be prepared for submission to the FDA.

Clinical investigators also have the authority to unblind their own SAE patients if/when the unblinded treatment information could impact the patient's clinical management. There is a module within the IRT system for investigators' use if "emergency" unblinding is required; however, the Investigator is requested to confer with the Medical Monitor before taking any action. The need for emergency unblinding is not expected for this study, in light of the nature of the study drug.

